# 4.1.4 Pharmacokinetic Population (for the PK Sub-Study Evaluations)

The PK population for each product use session will include subjects who used a product and have evaluable PK profiles. This population will include approximately half (up to 20 out of 40) of the subjects from each of the four *my*bluTM arms and from the Cigarette arm, plus all subjects (20) from the JUUL® arm. The sub-study will therefore include approximately 120 subjects, of which 100 subjects would also participate in the main study and 20 subjects (the JUUL® arm) exclusively in the substudy.

#### 4.2 Preliminary Data and Interim Analysis

Preliminary analyses may be performed, as judged applicable.

#### 5. PRODUCT DESCRIPTIONS

All subjects will be required to provide a sufficient supply of their usual brand combustible cigarettes to the study site for use on Day 1.

Each subject's usual brand information, including Universal Product Code (UPC) number, will be documented.

The following investigational products will be used during the study:

- mybluTM system with Tobacco Chill flavor Intense Liquidpod, 2.5% nicotine
- mybluTM system with Tobacco Chill flavor Intense Liquidpod, 4.0% nicotine
- mybluTM system with Honeymoon flavor Intense Liquidpod, 2.5% nicotine
- mybluTM system with Honeymoon flavor Intense Liquidpod, 4.0% nicotine

Each blu e-liquid contains a mixture of glycerin, propylene glycol, nicotine, and a proprietary blend of flavors.

The following comparator products will be used during the study:

- Subject's usual brand combustible cigarette
- JUUL® system with Virginia Tobacco Flavor JUULpod, 5.0% nicotine

In the CSR text and table headings, product use will be referred to by the short descriptions; the 6 products referred to as Products A-F and table footers by the long description in the following table:

**Table 5.1. Product Description** 

Arm	Products	Short Description	Format	Long Description
	A	myblu™ Tobacco Chill 2.5%	e-cigarette	my blu ™ closed system with CF Cosmic Fog Tobacco Chill flavor, nicotine salt liquid 2.5 %
A	В	myblu™ Tobacco Chill 4.0%	e-cigarette	myblu™ closed system with CF Cosmic Fog Tobacco Chill flavor, nicotine salt liquid 4.0%
	С	my blu™ Honeymoon 2.5%	e-cigarette	my blu ™ closed system with CF Cosmic Fog Honeymoon flavor, nicotine salt liquid 2.5 %
	D	my blu™ Honeymoon 4.0%	e-cigarette	my blu ™ closed system with CF Cosmic Fog Honeymoon flavor, nicotine salt liquid 4.0%
В	B I E I Cigarette I		combustibl e cigarette	Subject's usual brand combustible cigarette
С	C F JUUL® e-c		e-cigarette	JUUL® system with Virginia Tobacco Flavor JUULpod, 5.0% nicotine

#### 6. ANALYSIS OF STUDY ENDPOINTS

# 6.1 Product Use and Compliance

#### **6.1.1 Product Use and Compliance Assessments**

#### mybluTM Product Use

Following product training on Day 1, subjects will use each of the four test products individually for approximately 2 hours each, with the order of use selected by the subject. Following the last 2-hour period, subjects may choose any of the e-liquids freely through 23:00 on Day 2. At 20:00 on Day 2, subjects will complete the *my*bluTM Product Preference Questionnaire. Initial product assignment for each subject will be made by the study statistician or designee. Beginning on the morning of Day 3, subjects will use the assigned e-liquid through Day 28 and will be given the opportunity at Visit 3 to switch to the alternate nicotine strength of their current flavor, to switch to the alternate flavor with the same nicotine strength as their initial choice, or to continue using the same e-liquid selected initially through Day 57 (Visit 5, last study day). Each day from Day 3 through discharge from the study on Day 57, subjects randomized to the *my*bluTM arm will self report their product use via a text message system (Medquest).

Subjects participating in the PK sub-study will continue to use the assigned product through the evening of Day 4. All pods used during the 24-hour urine collections will be weighed within 24 hours before and after use, with the weights documented. On Test Visit 3 (Day 28) and Test Visit 5 (Day 56) as well, all pods used during the 24-hour urine collections will be weighed within 24 hours before and after use, with the weights documented.

#### **Usual Brand Cigarette Use**

Subjects randomized to the continue-smoking arm will smoke their usual brand cigarettes at home and throughout each confinement visit, and will self-report the number of cigarettes smoked each day from Day 3 through discharge from the study via a text message system.

# JUUL® Product Use

Subjects in the JUUL® arm will begin using the product following the demonstration and training on Day -2 and will continue to use the product through 23:00 on Day -1.

#### **Product Use Compliance**

Subject self-reported product use will be used as a measure of compliance. The clinic staff will monitor the frequency with which subjects complete the daily product use entries leading up to each Test Visits 2 through 5.

Biochemical verification of compliance will also be performed. Exhaled CO and urine cotinine will be used as methods of verifying compliance in real-time.

NNAL is a tobacco-specific nitrosamine with a longer half-life than CO, thus may provide an estimate of compliance over a long period of time by comparison of the post-baseline values to the baseline values. As this will be measured in a bioanalytical assay, real-time monitoring will not be possible and the verification will be completed at the end of the study.

NNAL will be considered as an additional exploratory variable for compliance.

#### 6.1.2 Product Use and Compliance Data Summarization

The following product use variables will be determined:

#### PK Sub-Study

- Number of puffs taken during each controlled and ad libitum product use session
- mybluTM and JUUL® pod weight change (only on Day 5 or Day 1, respectively)

#### In-clinic

- Number of cigarettes smoked
- Number of *my*bluTM pods started

- mybluTM pod weight change (for pods used during the 24 hour urine collections)
- Day 3 and Day 29 product preference selection (a listing)

# Self report

- Number of cigarettes smoked (*my*bluTM and cigarette arms)
- Number of *my*bluTM pods started (*my*blu arm)
- > 50 puffs taken from of mybluTM product (Y/N) (mybluTM arm)

#### Compliance

- $\geq$  90% reduction of cigarette use from baseline (*my*bluTM arm)
- $\geq 70\%$  daily product use reporting (yes/no) all cohorts
- Measured eCO (≤8 ppm) all cohorts
- $\geq 75\%$  reduction in post-baseline urine NNAL from baseline (*my*bluTM arm)
- Urine cotinine (yes/no) all cohorts

All product use data (including the number of puffs and including the PK product use sessions) and compliance variables will be summarized by study product using descriptive statistics (by time point, day, and product use session as appropriate) but no statistical comparisons will be made. The difference in weight before and after use of each e-cigarette (Products A to D and Product F) will be summarized.

For the PK sub-study, the number of puffs and the difference in weight before and after use of each e-cigarette will also be summarized.

The level of precision for each statistic will be presented as follows:

- minimum/maximum in same precision as the data,
- arithmetic mean/median in one more level of precision than minimum/maximum,
- SD in one more level of precision than mean/median,
- n will be presented as an integer,
- arithmetic CV% will be presented to 1 decimal point, and

# 6.2 Biomarkers of Exposure and Potential Harm

#### **6.2.1** Biomarker Sample Collection

#### **Blood Biomarker Sample Collection**

Blood samples for COHb in whole blood (2 x 4 mL), sICAM in plasma (1 x 4 mL), WBCs in whole blood (measured in hematology sample), HDL-C in serum (1 x 3.5 mL), MCP-1 in serum (1 x 3.5 mL), and serum for bio-banking (up to 17 mL) will be collected during Test Visit 1 (on Days -2, and -1), Test Visit 3 (Days 28 and 29), and Test Visit 5 (Days 56 and 57). Samples for COHb will be collected in the afternoon

and samples for the other biomarkers and bio-banking will be collected following an overnight ITTt of at least 8 hours.

### **Urine Biomarker Sample Collection**

24-hour urine collections for biomarker measurements (NNAL, 3-HPMA, S-PMA, NNN, CEMA, HEMA, HMPMA, MHBMA, 1-OHP, (-tol, 3-OH B[a]P, 1-AN, 2-AN, nicotine equivalents, 8-epi-prostaglandin  $F_{2\alpha}$ , and 11-dehydrothromboxane  $B_2$ ) will take place, as applicable, during Test Visit 1 (on Days -2, -1, 3, and 4), Test Visit 3 (Days 28 and 29), and Test Visit 5 (Days 56 and 57). Each 24-hour urine collection will begin at a time following check-in and will end at the same time  $\pm$  30 minutes the following day.

Subjects will be instructed to attempt to void prior to the beginning and at the end of each interval. All urine must be collected during the entire 24-hour interval. The start and stop time of each 24-hour interval and the total weight of the collection will be documented. The weight of the 24-hour urine collection containers will be documented prior to the collection (tare weight) and following completion of the collection.

Collections for each subject will be pooled into one labeled container throughout the interval and the total weight (g) will be recorded at the end of the 24-hour interval. Any missed voids will be documented, including the reason for missing.

#### 6.2.2 Biomarker Calculations

#### **Calculation of Urine Nicotine Equivalents**

Nicotine equivalents will be calculated as the molar sum of nicotine and 5 major nicotine metabolites. Values of individual components reported as below the limit of quantitation (BLQ) will be set to one-half of the limit of quantitation in the calculation below. Missing urine data will not be imputed.

Nicotine equivalents ( $\mu$ g/mL) = (nicotine [ng/mL]/162.23 [mg/mmol] + nicotine-gluc (ng/mL)/338.36 [mg/mmol] + cotinine [ng/mL]/176.22 [mg/mmol] + cotinine-gluc [ng/mL]/352.34 [mg/mmol] + trans-3'-hydroxycotinine [ng/mL]/192.22 [mg/mmol] + trans-3'-hydroxycotinine-gluc [ng/mL]/368.34 [mg/mmol]) x 162.23 (mg/mmol) x 1  $\mu$ g/1000 ng

#### **Calculation of Total Mass Excreted**

Urine biomarker concentrations will be converted into biomarker quantities excreted in 24 hours by multiplying the measured concentration by the total weight (i.e., 1 kilogram = 1 liter) of urine produced by the subject during the 24-hour period.

#### **Creatinine Adjustments**

Urine creatinine will be measured and used to adjust the values of the primary and secondary urine BoPH and BoE as follows.

Biomarker =  $\underline{\text{Biomarker (units) x 100}}$ (unit/g creatinine) =  $\underline{\text{creatinine (mg/dL)}}$ 

#### 6.2.3 Biomarker Data Summarization

Biomarker concentrations reported as below the limit of quantitation will be reported as "BLQ" in the listings and set to one-half of the limit of quantitation for summarization and statistical analysis.

The following variables will be determined and summarized for each urine biomarker.

- Measured concentration
- Total biomarker mass excreted per 24 hours
- Creatinine-adjusted excretion level

Absolute and percent change-from-baseline will be determined for the mass excreted and creatinine-adjusted values. The total urine biomarker mass excreted per 24 hours change-from-baseline value will be used in the statistical analysis.

Data will be listed by subject, product, and visit or day (and time point as applicable) and summarized by product and visit or day (and time point as necessary). Absolute and percent change-from-baseline values, and absolute and percent differences between Test Visits 3 and 5 (Days 28 and 56, respectively), will also be listed and summarized where indicated.

Descriptive statistics (number of observations, mean, median, standard deviation, standard error of the mean, CV%, minimum, and maximum) will be presented. Figures will be used to display the data graphically as applicable. All data summarizations and figures will be generated using the ITT population. In addition, PP population will also be used for the primary biomarkers only: COHb in plasma and NNAL, 3-HPMA, and S-PMA in urine. Data summarizations and statistical analyses will be performed using SAS procedures. Statistical analyses are described in Section 6.7.

#### 6.3 Physiologic Assessments

#### **6.3.1** Physiologic Assessments and Visits

Test Visit 1, 3, and 5 check-in blood pressure (systolic and diastolic) and heart rate measurements will be assessed for physiologic assessment purposes.

#### 6.3.2 Data Summarization for Physiologic Assessments

Data will be listed by subject, product, and visit or day (and time point as applicable) and summarized by product and visit or day (and time point as necessary). Absolute and percent change-from-baseline values, and absolute and percent differences between Test Visits 3 and 5, will also be listed and summarized, as applicable.

Descriptive statistics (number of observations, mean, median, standard deviation, standard error of the mean, CV%, minimum, and maximum) will be used for continuous data variables and frequency counts (number of observations and percentage) for categorical data variables.

Figures may be used to display the data graphically, as applicable. All data summarizations including figures will be generated using the ITT population. Data summarizations and statistical analyses will be performed using SAS procedures. Statistical analyses are described in Section 6.7.

# 6.4 Subjective Measures

#### **6.4.1** Subjective Effects Questionnaire

The PSCDI/PSECDI, Cough Questionnaire, QSU-Brief, MTWS-R, PES, Product Liking Questionnaire, Future Intent to Use Questionnaire, and Product and Health Effect Perceptions Questionnaire will be completed during Test Visit 1 (Day -2), Test Visit 3 (Day 28), and Test Visit 5 (Day 56), as applicable, using an electronic device. The QSU-Brief, MTWS-R, PES, and Product Liking Questionnaire will also be completed on Day 3 (Visit 1).

# 6.4.2 Subjective Effects Data Summarization

The following total scores, factor scores, and subscales will be calculated and summarized. For questionnaires without total scores, factor scores, or subscales (Cough Questionnaire, Product Liking Questionnaire, Future Intent to Use Questionnaire, and Product and Health Effect Perceptions Questionnaire), each item on the subjective measures questionnaires will be summarized.

- PSCDI/PSECDI total score
- MTWS-R total score
- QSU-brief factor scores:
  - Factor 1 (anticipation of pleasure from smoking) average of items 1, 3, 6, 7, and 10
  - o Factor 2 (relief of nicotine withdrawal) average of items 2, 4, 5, 8, and 9
- PES subscales:

- o Satisfaction average of items 1, 2, 3, and 12
- Psychological reward average of items 4 through 8
- o Aversion average of items 9, 10, 16, and 18
- o Relief average of items 11, 13, 14, 15, and reversed for item 20
- o Items 17, 19, 21 will be summarized as individual item scores.

Data will be listed by subject, product, and visit or day (and time point as applicable) and summarized by product and visit or day (and time point as necessary). Absolute and percent change-from-baseline values, and absolute and percent differences between Test Visits 3 and 5, will also be listed and summarized, as applicable. Baseline is the last no-missing observation collected prior to Day 1 product use.

Descriptive statistics (number of observations, mean, median, standard deviation, standard error of the mean, CV%, minimum, and maximum) will be used for continuous data variables and frequency counts (number of observations and percentage) for categorical data variables.

Figures may be used to display the data graphically, as applicable. All data summarizations including figures will be generated using the ITT population. Data summarizations and statistical analyses will be performed using SAS procedures. Statistical analyses are described in Section 6.7.

#### 6.5 Plasma Nicotine Pharmacokinetics

#### 6.5.1 Measurements and Collection Schedule

PK assessments will take place on Day 1 for the JUUL® and continue-smoking arms, and on Day 5 for the *my*bluTM arm. A 4 mL blood sample for plasma nicotine analysis will be drawn into a plastic K2-EDTA (lavender top) vacutainer tube approximately 5 minutes prior to and at 3, 5, 7, 10, 12, 15, 20, 30, 60, 120 and 180 minutes following the start of each product use episode (fixed/controlled and *ad libitum*).

#### 6.5.2 Pharmacokinetic Concentrations

Plasma concentrations of nicotine as determined at the collection times described in Section 6.2.1 will be used for the calculation of the plasma nicotine PK parameters.

All concentration data will be included in the calculation of the individual PK parameters, the individual concentration-time plots (based on actual sample times), and in the mean concentration-time plots (based on nominal sample times). However, if there are any significant deviations from nominal sample times, some concentration data may be excluded from mean concentration-time plots and/or additional concentration-time plots of the mean data may be provided. All deviations and excluded data will be provided and discussed in the CSR.

#### 6.5.3 Plasma Nicotine Pharmacokinetic Parameters

The appropriate noncompartmental PK parameters will be calculated for each product use episode (controlled and *ad libitum*) from the baseline adjusted plasma nicotine concentration-time data using Phoenix® WinNonlin® Version 7.0 or higher. Actual sample times will be used in the calculations of the PK parameters. The calculation of the actual time for nicotine will be in respect to the start of product use episodes on Day 1 for the JUUL® and continue-smoking arms, and on Day 5 for the *my*bluTM arm. All PK parameters included in the protocol are listed in Table 6.1 below, and are defined as appropriate for study design.

Table 6.1. Noncompartmental Pharmacokinetic Parameters to be Calculated (Baseline Adjusted)

Label to be Used in the Text, Tables and Figures	Definition	Method of Determination
AUC0-t	Area under the nicotine concentration-time curve from time 0 (defined as the start of product use) to 180 minutes (or the last quantifiable concentration during the interval)	Calculated using the Linear Trapezoidal with Linear Interpolation Method
Cmax	Maximum measured plasma concentration over the duration of the measurement interval	Taken directly from bioanalytical data
Tmax	Time to reach the maximum measured plasma concentration over the duration of the measurement interval. If the maximum value occurs at more than one time point, Tmax is defined as the first time point with this value.	Taken from clinical database as the difference in the time of administration and the time of the blood draw which is associated with the Cmax.

Pharmacokinetic parameters will not be calculated for subjects with less than 3 consecutive post-product use time points with quantifiable concentrations. Subjects for whom there are insufficient data to calculate the PK parameters will be included in the concentration tables only and excluded from the descriptive statistics.

For the calculation of the PK parameters, plasma concentrations that are BLQ will be set to one-half of the LLOQ for the calculation of descriptive statistics of unadjusted plasma nicotine concentrations. Baseline adjustments (pre-product use) will be performed for calculation of PK parameters. The values used for all pre-product use adjustments is the plasma nicotine concentration value obtained before the first product use on Day 1-6 and the adjustment will be subject-specific.

Baseline-adjustment method: For each PK profile, the pre-product administration nicotine concentration value for each subject will be subtracted from each nicotine concentration obtained after test product administration on that day/episode using the following equation:

$$C_t = C_{t \text{ uncorrected}} - [C_0 \cdot e^{-Kel \cdot t1}]$$

Where:

 $C_t$  = Corrected concentration.

 $C_{t \text{ uncorrected}}$  = the uncorrected concentration.

 $C_0$  = the pre-product administration concentration.

$$Kel = \frac{\ln(2)}{t_{1/2}}$$

Where t1/2 is 2.0 hours for all subjects (estimated nicotine half-life)

t = actual sampling time since product administration.

t1 = actual sampling time since pre-product administration sampling.

After correction for pre-product administration values, some concentrations may be below the lower limit of quantitation and some may be negative values. Negative values will be assigned a value of zero in the analyses and all other values obtained will be reported as is even if these values are BLQ.

#### 6.5.4 PK Data Summarization and Presentation

All nicotine PK concentrations and/or PK parameters descriptive statistics will be generated using SAS® version 9.4 or higher.

The plasma concentrations of nicotine will be listed and summarized by product, product use episode, and time point for all subjects in the PK Population. Unadjusted and baseline adjusted plasma concentrations of nicotine will be presented with the same level of precision as received from the bioanalytical laboratory. Summary statistics, including number of observations (n), arithmetic mean (Mean), standard deviation (SD), coefficient of variation (CV%), minimum, median, maximum will be calculated for all nominal concentration time points. Excluded subjects will be included in the concentration listings, but will be excluded from the summary statistics and noted as such in the tables. All BLQ values will be presented as "BLQ" in the concentration listings and footnoted accordingly.

Mean and individual concentration-time profiles will be presented on linear and semilog scales. Linear mean plots will be presented with and without SD.

Plasma nicotine PK parameters will be listed and summarized by product, product use episode, and time point for all subjects in the PK Population. Pharmacokinetic parameters will be reported to 3 significant figures for individual parameters, with the exception of Tmax, which will be presented with 2 decimal places. Summary statistics (n, arithmetic mean, geometric mean, SD, CV%, geometric CV% (Geom CV%), minimum, median, maximum), will be calculated for plasma nicotine PK parameters AUC0-t, Cmax, and Tmax. Excluded subjects will be listed in the PK parameter tables, but will be excluded from the summary statistics and noted as such in the tables.

The level of precision for each concentration and PK parameter statistic will be presented as follows:

- minimum/maximum in same precision as in bioanalytical data and/or parameter output,
- mean/geometric mean/median in one more level of precision than minimum/maximum,
- SD in one more level of precision than mean/median,
- n will be presented as an integer, and
- CV% and Geom CV% will be presented to the nearest tenth.

Statistical analyses will be performed using SAS and are described in Section 6.7.

# 6.6 Urge to Smoke

#### **6.6.1** Urge to Smoke Parameters

Urge to smoke will be assessed using a 100 mm VAS approximately 10 minutes prior to and within approximately 30 seconds prior to the scheduled blood draws at 5, 10, 15, 30, 60, and 120 minutes following the start of the *ad libitum* product use session.

The following parameters will be calculated for the urge to smoke assessments performed during the PK assessments.

 $E_{max\_R}$  The maximum reduction from baseline VAS score (VASpre-use – VASpost-use).

TEmax Time of the  $E_{max\_R}$ . If the maximum value occurred at more than one time point,  $TE_{max}$  will be defined as the first time point with this value.

AUEC\_0-120\_R The area under the reduction from baseline "Urge to Smoke" VAS score (VASpre-use – VASpost-use) versus time curve from 0 to 120 minutes, calculated using the linear trapezoidal method with linear interpolation using actual sample times

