6.7.3 Urge to Smoke Assessment

Urge to smoke will be assessed using a 100 mm VAS (Appendix 11) approximately 10 minutes prior to and within approximately 30 seconds prior to the scheduled blood draws at 5, 10, 15, 30, 60, and 120 minutes following the start of the *ad libitum* product use sessions.

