7.4.6 Urge to Smoke Parameters

The following parameters will be calculated for the urge to smoke assessments performed during the PK assessments.

E _{max_R}	The maximum reduction from baseline VAS score (VASpre-use – VASpost- use). If there is no reduction, a value of zero will be reported.
TE _{max}	Time of the E_{max_R} . If the maximum value occurred at more than one time point, TE_{max} will be defined as the first time point with this value.

AUEC_0-120 The area under the change from baseline "Urge to Smoke" VAS score versus time curve from 0 to 120 minutes, calculated using the linear trapezoidal method with linear interpolation using actual sample times.

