# Statistical Analyses of Pharmacokinetics (*my*bluTM Products Versus the Continuesmoking arm or JUUL arm)

A linear mixed model ANOVA will be performed on the log-transformed nicotine PK parameters AUC and Cmax from each product use session (PK population). The model will include product arm as a fixed effect. Geometric LSMs will be provided for the PK parameters of Cmax and AUC by product arm. Geometric LSM ratio, 95% confidence intervals of geometric LSM ratio, and p-values will be provided for the product arm comparisons for Cmax and AUC. The comparisons of interest will include each of the *my*bluTM product arms compared to continue-smoking arm or JUUL arm. The above statistical analyses will be performed using the following SAS codes.

```
Proc MIXED data=<>;
Class subject arm;
Model LN_dependent variable = arm/DDFM=KR;
LSMeans arm/pdiff CL alpha=0.05;
Run;
```

Non-parametric analysis (Wilcoxon Rank Sum test) will be performed for the comparisons of  $T_{max}$  between test and reference products.

Similar methods will be used to compare the urge to smoke parameters.

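### SAP 6.6.1 assigns a TE_max to subjects whose urge to smoke never falls, so the recorded time is not a time of relief and can distort the product comparison

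*SAP*

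**What the plan says.** SAP 6.6.1 defines E_max_R as "The maximum reduction from baseline VAS score (VASpre-use – VASpost-use"), and TE_max as the time of E_max_R. For ties it continues: "If the maximum value occurred at more than one time point", TE_max "will be defined as the first time point with this value". Post-use scores are taken just before the "scheduled blood draws at 5, 10, 15, 30, 60, and 120 minutes following the start of the" ad libitum session, so 5 minutes is the smallest value TE_max can take and 120 the largest (nominal times).

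Protocol 7.4.6 has the same tie rule but adds a floor for E_max_R: "If there is no reduction, a value of zero will be reported". It does not say what TE_max is in that case. The SAP omits the floor. SAP Section 8 nevertheless reports no departure from the protocol analyses.

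TE_max is a listed secondary endpoint in both documents. SAP 6.6.2 summarises it in the PK population, with no exclusion for lack of relief. SAP 6.7.2 compares each myblu product with the cigarette and with JUUL, saying only: "Similar methods will be used to compare the urge to smoke parameters". The shell for Table 14.2.5.13 in SAP 10.2 is shared with AUC and Cmax and uses log-transformed values and geometric means.

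**The concern.** A time to maximum reduction has meaning only if there was a reduction. As written, the rule returns a number for every subject with data, including one with no relief and one with no urge to relieve (VAS 0 before use). Such subjects enter the same summary and the same test as those who were relieved.

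The plan takes this care elsewhere. SAP 6.5.3 withholds nicotine PK parameters, T_max included, from subjects with too few consecutive quantifiable concentrations. TE_max has no equivalent condition. With up to 20 subjects per product in the sub-study, a handful of such values can move a median or a rank test.

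**Working it through.** The documents give no expected value, power or sample size for TE_max, so there is no planned figure to reproduce.

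**Step 1. Apply the SAP definition literally.** For pre-use score V0 and post-use scores V(t) at t = 5, 10, 15, 30, 60, 120: E_max_R = max of [V0 − V(t)], and TE_max = the first t attaining it.

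| Profile (illustrative) | E_max_R, SAP | E_max_R, protocol | TE_max, SAP |
|---|---|---|---|
| Flat at 80, at 100, or at 0 | 0 | 0 | 5 min |
| From 60, rising steadily from 62 to 95 | −2 | 0 | 5 min |
| From 60: 80, 78, 75, 70, 65, 62 | −2 | 0 | 120 min |
| Above baseline except equal to it at 60 min | 0 | 0 | 60 min |

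The tie rule drives only the flat rows. In the second and third rows the missing floor does the work: the time of least worsening is taken as the time of maximum reduction.

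**Step 2. How often 5 minutes results.** Among simulated subjects without relief, the share recorded at 5 minutes was 100% if profiles are flat or steadily rising, about 18–22% if worsening has no time trend, and 30–53% with an upward drift of 5–20 mm over 120 minutes plus noise of SD 5 mm. All these shapes are assumptions.

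**Step 3. Effect on a rank comparison.** Assume relievers' TE_max over the six times is distributed as .30/.30/.20/.15/.05/0 for the cigarette and .15/.25/.25/.20/.10/.05 for myblu. For a myblu subject recorded at each time in turn, the probability of being later than a cigarette subject (ties counted half) is .15, .45, .70, .875, .975, 1.

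- Relievers only: .15×.15 + .25×.45 + .25×.70 + .20×.875 + .10×.975 + .05×1 = 0.6325.
- Now let a share f of myblu subjects, and no cigarette subjects, lack relief. The probability is (1 − f)×0.6325 + f×m, where m is set by where non-relievers are recorded.

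As an illustrative f, Protocol 1.2 reports a relief item (1–7 scale) with mean 3.5, SD 1.98 for the 25 mg salt product. A normal approximation to the bottom category gives z = (1.5 − 3.5)/1.98 = −1.01, or about 16%. For the cigarette (5.5, SD 1.60), z = −2.5, or about 1%, taken as zero here.

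| Non-relievers recorded at | m | Result, f = 0.16 |
|---|---|---|
| All at 5 min | .15 | .5313 + .0240 = 0.56 |
| 40% at 5 min, rest evenly over the other five times | .54 | .5313 + .0864 = 0.62 |
| Evenly over all six | .692 | .5313 + .1107 = 0.64 |
| All at 120 min | 1 | .5313 + .1600 = 0.69 |

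The artefact can lie on either side of 0.63.

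**Step 4. False differences.** A rank-sum test was simulated with 20 v 20, two-sided 0.05, and identical TE_max distributions among relievers in both products. Product A had subjects without relief; the comparator had none.

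- All of A's non-relievers at 5 minutes, relievers mostly peaking at 15–30 minutes: A was significantly faster in 6, 13, 28, 50 and 78% of runs at 10, 20, 30, 40 and 50% without relief (nominal 2.5%).
- The same, but with 60% of relievers peaking at 5 minutes: 4, 6, 11, 16 and 23%.
- One sixth of non-relievers at 5 minutes, 40% without relief: A faster in 1.3% and slower in 3.6% of runs with late-peaking relievers; A slower in 26% with early-peaking relievers.
- TE_max left missing without a reduction (40% case, late-peaking relievers): about 2% each way.

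**The case against.** The strongest reply is that the effect is conditional, visible and confined to one parameter. Much of this stands.

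- A reader might infer that every subject without relief is scored as fastest, so the rule favours the product that relieves fewest people. The documents do not support that: Step 1 shows a value of 120 minutes, and Steps 3 and 4 show the bias vanishing or reversing. Exact ties on a 100 mm scale need not be common.
- Under the protocol wording, a subject whose post-use scores all exceed baseline has E_max_R set to zero at no observed time. TE_max is then undefined, not 5 minutes.
- The 16% is a weak proxy. It comes from a 15-subject crossover with ten fixed puffs and one rating at about 20 minutes. The present session is ad libitum, uses a preference-based product, and takes the best of six scores. No share can be derived for JUUL.
- E_max_R and AUEC would still show lack of relief, and the by-subject parameter tables would show a TE_max beside a zero or negative E_max_R.
- TE_max is a time of maximum reduction, and neither document says that shorter is better.
- The rank-sum test is not fixed for TE_max.

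None of this makes the recorded value valid. Visibility in a listing does not remove it from the summary or the test, and the unnamed test is a further gap.

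**Conclusion.** The point holds as a defect of definition. SAP 6.6.1 returns a TE_max where there was no reduction, and for flat or steadily rising profiles that value is the minimum of 5 minutes. No other section of the SAP corrects this. The zero floor for E_max_R was dropped without being declared.

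The size is not determinable from the documents. In the example it ranges from 0.56 to 0.69 around 0.63. False significance ranges from no material excess to 78% at the most extreme setting tried, with half of one product's subjects unrelieved and all recorded at 5 minutes. These figures rest on assumed reliever distributions, no-relief shares and profile shapes. A fixed direction, or a stated loss of power, would claim more than the documents allow.

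**What to change.** - **SAP 6.6.1:** restore the protocol's zero floor for E_max_R, or declare its removal in SAP Section 8. Define TE_max only when E_max_R is above zero, and set it to missing otherwise.
- **Tables 14.2.5.7 to 14.2.5.13:** report the number and percent of subjects with no reduction, by product, beside the TE_max results.
- **SAP 6.7.2 and the shell for Table 14.2.5.13:** state that TE_max is compared by the Wilcoxon rank-sum test used for T_max, not in the log-transformed format. That format also cannot accept an E_max_R of zero or below.
- **Optional sensitivity analysis:** rank subjects without relief last. This mixes whether relief occurred with when it peaked, so it should not be the main analysis.

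The cost is a few sentences and one table row. The TE_max comparison would then use only subjects with some relief, so it has slightly fewer subjects and must be read together with the no-relief count.
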